LIST OF ABBREVIATIONS AND RELEVANT DEFINITIONS

ABR General Assessment and Registration form (ABR form), the application

form that is required for submission to the accredited Ethics Committee; in

Dutch: Algemeen Beoordelings- en Registratieformulier (ABR-formulier)

AE Adverse Event

AR Adverse Reaction

CA Competent Authority

CCMO Central Committee on Research Involving Human Subjects; in Dutch:

Centrale Commissie Mensgebonden Onderzoek

CV Curriculum Vitae

DSMB Data Safety Monitoring Board

EU European Union

EudraCT European drug regulatory affairs Clinical Trials

GCP Good Clinical Practice

GDPR General Data Protection Regulation; in Dutch: Algemene Verordening

Gegevensbescherming (AVG)

IB Investigator's Brochure

IC Informed Consent

IMP Investigational Medicinal Product

IMPD Investigational Medicinal Product Dossier

METC Medical research ethics committee (MREC); in Dutch: medisch-ethische

toetsingscommissie (METC)

(S)AE (Serious) Adverse Event

SPC Summary of Product Characteristics; in Dutch: officiële productinformatie

IB1-tekst

Sponsor The sponsor is the party that commissions the organisation or performance

of the research, for example a pharmaceutical

company, academic hospital, scientific organisation or investigator. A party

that provides funding for a study but does not commission it is not

regarded as the sponsor, but referred to as a subsidising party.

SUSAR Suspected Unexpected Serious Adverse Reaction

UAVG Dutch Act on Implementation of the General Data Protection Regulation; in

Dutch: Uitvoeringswet AVG

WMO Medical Research Involving Human Subjects Act; in Dutch: Wet Medisch-

wetenschappelijk Onderzoek met Mensen

UCL Ulnar collateral ligament

V7 01-02-2024 6 of 30

MHQ Michigan Hand Outcomes Questionnaire

PSFS Patient Specific Functional Scale

ED Emergency department

RCT Randomized controlled trial

SD Standard deviation

MCID Minimal clinically important difference

ISS Injury Severity Score

CTS Carpal tunnel syndrome

MCP Metacarpophalangeal

CMC Carpometacarpal

IP Interphalangeal

ADL Activities of daily living

ICHOM International Consortium for Health Outcomes Measurement International

CUA Cost-utility analysis
CEA Cost-effectiveness

QALY Quality adjusted life year

V7 01-02-2024 7 of 30

SUMMARY

12 months.

Rationale: Guidelines recommend surgery for complete Ulnar Collateral Ligament (UCL) ruptures, including Stener lesions. This recommendation is based on expert opinion, anatomic theories and low quality observational case series. High quality studies comparing cast immobilization with operative treatment are lacking. We hypothesize that cast immobilization is non-inferior regarding functional outcome and carries concomitant lower costs compared with operative treatment for complete UCL ruptures, including Stener Lesions.

Objective: To compare functional outcomes and cost-effectiveness of cast immobilization with immediate surgical treatment.

Study design: Multicenter randomized controlled trial (RCT) with 12 months follow-up. **Study population:** Adult patients of 18 years and above, requiring treatment for an acute complete UCL rupture, including Stener Lesions.

Intervention: Non-operative treatment with a cast to immobilize the thumb. After 2 weeks the thumb will be re-examined to determine if surgery is required. It is expected that at re-evaluation at 2 weeks after starting the cast treatment about 1 in 10 patients will still need surgery. The intervention is compared to surgery, which is standard treatment.

Main study parameters/endpoints: Hand function expressed as the Michigan hand outcome questionnaire (MHQ) score at 6 months (from date of injury to 6 months after).

Nature and extent of the burden and risks associated with participation, benefit and group relatedness: It is expected that about 1 in 10 patients who started with cast immobilization will need surgery during re-evaluation at 2 weeks after starting the cast immobilization, meaning completing the treatment will take 2 weeks more for these patients. Patients need to fill in questionnaires, which takes about 2 hours (maximum) over a period of

V7 01-02-2024 8 of 30

1. INTRODUCTION AND RATIONALE

In the Netherlands, approximately 10,500 patients are diagnosed with an acute ulnar collateral ligament (UCL) injury of the thumb yearly. These UCL injuries are classified into 3 grades based on the laxity of the ligament. Grade 1 injuries present with tenderness along the UCL, without laxity compared with the non-injured thumb. They are classified as sprains and have an intact UCL. Grade 2 injuries demonstrate an increase in laxity, but have a firm endpoint which indicates a partial rupture of the UCL. Grade 3 injuries are complete UCL ruptures with increased laxity without a firm endpoint. Around 75% of UCL injuries are complete UCL ruptures. These complete UCL ruptures include Stener Lesions, meaning an interposition of a part of a thumb muscle between the torn ligament ends. The prevalence of Stener Lesions varies widely between studies, ranging from 11 to 87%. [1] Dutch guidelines drafted by the society of Surgery and Plastic Surgery, recommend immobilization of the thumb with a cast for 4-6 weeks for grade 1 and 2 injuries. For complete UCL ruptures, they recommend surgery followed by cast immobilization. This recommendation is based on expert opinion, anatomic theories and low quality observational case series, mainly level-IV evidence. High quality studies comparing cast immobilization with operative treatment are lacking.

Outcomes of surgery for complete UCL ruptures, including Stener Lesions, are generally good regardless of the surgical technique. Regarding nonoperative treatment, two observational studies that evaluated thumb immobilization with a cast for complete ruptures, including Stener Lesions, showed promising results: in 71 patients who underwent cast immobilization, 63 (89%) felt normal or had minimal disability after 1 year. Those who remained symptomatic were successfully treated with surgery. [2,3] One patient remained symptomatic after surgery (percentage is similar to patients treated with initial surgery). Taking those studies into account, a nonoperative treatment strategy for complete UCL ruptures, including Stener Lesions, after which patients only have a small chance of secondary surgery, could be justified. Nonoperative treatment with cast immobilization is minimal invasive and could lead to lower costs compared to operative treatment. Therefore, we want to conduct a RCT with non-inferiority design comparing functional outcomes and cost-effectiveness of cast immobilization, only followed by operative treatment in case of persistent laxity after 2 weeks of cast immobilization, with immediate operative treatment

V7 01-02-2024 9 of 30

2. OBJECTIVES

[figure not shown]
Primary Objective: to evaluate hand function expressed as the MHQ score at 6 months (from date of injury to 6 months after).

Secondary Objectives: to evaluate patient reported hand function and activities of daily life with the Patient Specific Functional Scale (PSFS) and MHQ, range of motion of the thumb joints, pinch/grip strength, pain, quality of life, patient satisfaction, patient expectation, complications, work-absence and cost-effectiveness up to 12 months.

V7 01-02-2024 10 of 30

3. STUDY DESIGN

Multicenter RCT to include 126 patients with 12 months follow-up to compare functional outcomes and cost-effectiveness of cast immobilization with surgical treatment. The study inclusion period is 30 months. Patients will be randomized by simple randomization. A flow diagram of the study is provided in figure 1.

^{**} counted as observed

Figure 1.

V7 01-02-2024 11 of 30

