4.4 Sample size calculation

This sample size calculation is based on our primary endpoint (hand function at 6 months expressed as MHQ score 6 months after injury) and calculated using G Power 3.1.9.2. The MHQ score of an individual without any complaints of the hand is 100. The lowest score, indicating worst pain and severe impairment, is zero. The hypothesis will be assessed using a non-inferiority design. The results from two earlier studies on the subject were used for sample size calculation. [4,5] We used a one-sided significance level of 0.025 and a power of 80% with a standard deviation (SD) of 15, and setting our non-

V7 01-02-2024 12 of 30

inferiority limit at 8. The non-inferiority limit of 8 is based on the previous estimated minimal clinically important difference (MCID) of 15 points, divided by 2 and rounded up to 8. A total of 114 patients will be needed to demonstrate non-inferiority of our hypothesis. Each treatment arm will need 57 patients. Including consideration for a potential 10% loss to follow-up, the total number of patients to be included, set at 114, is multiplied by a factor of 1.10. This results in a total of 126 patients to be included.". The MCID of 15 is based on the average of the MCID's of 23, 13 and 8 for the pain, function and work domains, respectively in patients with carpal tunnel syndrome (CTS). [4] The MCID in MHQ score for patients with thumb injury is not yet investigated. Therefore, we decided to use the MCID of CTS patients.

Considering the uncertain outcome of the control group treatment in terms of MHQ-scores for patients with UCL-ruptures, an independent statistician will assess if the sample size calculation needs adjustment, based on the mean change in MHQ-score and SD in the control group, after half of the patients past their 6-month follow-up (N=28).

V7 01-02-2024 13 of 30

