- When the hand surgeon concludes that there is a firm endpoint (meaning adequate healing of the UCL ligament) cast immobilization is continued for another 2 weeks, until a total immobilization period of 4 weeks is completed. An appointment is scheduled after 4 weeks of cast immobilization.
- When there is no firm endpoint of the UCL or there is doubt about a firm endpoint, patients are scheduled for surgery within 5 working days (switching to usual care; see description usual care).

4) Outpatient clinic visit after 4 weeks of immobilization

The patient visits the hand surgeon. The immobilization cast is removed and replaced for a removable cast, which allows the patient to start exercising. Patients are instructed to start using the thumb for regular daily activities, without putting pressure on it, and start thumb exercises consisting of a combination of opposition and abduction/adduction movements. Patients are advised to repeat the exercises 5-10 times a day. A referral is made to the hand therapist to guide this process. Hand therapy will start within 1 week. The frequency and duration of hand therapy will be determined by the hand therapist. Hand therapists from all hospitals will collaborate to achieve consensus on a treatment protocol. Outcome measures are evaluated in the form of physical examination and surveys. A new appointment is scheduled at 3 months.

- 5) Visit to outpatient clinic at 3 months (standard visit)
 Progression of treatment is evaluated with the patient and expectations are managed.
 Outcome measures are evaluated in the form of physical examination and surveys. A new appointment is scheduled at 6 months.
- 6) Visit to outpatient clinic at 6 months (standard visit)
 Progression of treatment is evaluated with the patient and expectations are managed
 Outcome measures are evaluated in the form of physical examination and surveys. A
 new appointment is scheduled at 12 months.
- 7) Visit to outpatient clinic at 12 months (visit for study purpose)

 Treatment outcome is evaluated for study purposes. Outcome measures are evaluated in the form of physical examination and surveys.

USUAL CARE/COMPARISON

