6.2 Randomization, blinding and treatment allocation

All consecutive patients meeting the inclusion criteria will be asked to participate in the study. After the first outpatient clinic visit informed consent will be obtained by the hand surgeon or the investigator of the study site. Computerized randomization will be performed as soon as written informed consent is provided, with Castor EDC. In trials comparing surgery with non-operative management, blinding of patients and surgeons is not possible and therefore randomization of this study is not blinded.

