7. STATISTICAL ANALYSIS

Data will be analyzed following intention-to-treat. Categorical variables will be presented as counts and percentages and continuous variables as median and interquartile ranges or mean and standard deviation based on the normality of the data. Differences in characteristics between groups will be compared using Fisher exact and Pearson's χ^2 tests for categorical variables, and Wilcoxon rank sum tests and unpaired t test will be used for continuous variables, where appropriate.

We will conduct a linear regression analysis for longitudinal data (i.e. a mixed model) in which we correct for relevant prognostic factors (age, sex, time between trauma and definite treatment, duration of hand therapy) and baseline scores of the Michigan Hand Questionnaire. In an additional step, we will correct for surgeons depending on the number of treating surgeons as well as the number of patients per treating surgeon. Results will be presented as differences between treatment and control with 95% Confidence intervals. The intervention will be labeled as non-inferior when the noninferiority margin of 8 lies outside the 95% CI of this difference, regarding the Michigan Hand Questionnaire measured at 6 months as our primary endpoint. In case missing data did not happen randomly, but was related to specific factors (e.g. more missing data for men than for women), we will correct for this. In an additional analysis, the absolute MHQ scores at 6 months will be adjusted for differences in baseline MHQ scores between the intervention and control group. The secondary outcomes: PSFS, EQ5D, ROM, Kapandji score, grip strength, pinch strength and pain will be analyzed in a similar manner. Differences between the two treatment groups in complication rates will be analyzed using the Chi-square test or the Fischer's Exact test (in case the expected incidence was less than five).

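### Simple randomisation with no hospital term in the primary model leaves hospital mix to chance and gives up a little precision

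*Protocol*

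**What the plan says.** Protocol section 3 describes a "Multicenter RCT to include 126 patients with 12 months follow-up" and fixes the allocation method: "Patients will be randomized by simple randomization". Section 6.2 adds only the system and the timing: "Computerized randomization will be performed as soon as written informed consent is provided, with Castor EDC". It also says that "blinding of patients and surgeons is not possible and therefore randomization of this study is not blinded". No blocking, stratification or minimisation appears anywhere, and the number of hospitals is not given.

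Section 7 lists the covariates of the primary mixed model: age, sex, time from trauma to definite treatment, duration of hand therapy and baseline MHQ. Hospital is not among them. As a further step, "we will correct for surgeons depending on the number of treating surgeons as well as the number of patients per treating surgeon". Neither the threshold for taking that step nor the form of the correction is stated.

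**The concern.** Hospital is known before allocation and could plausibly influence the result. After allocation, the two-week re-examination that decides whether a cast patient goes on to surgery is a surgeon's manual judgement. On hand therapy, section 5.1 says "The frequency and duration of hand therapy will be determined by the hand therapist". Yet hospital is used neither in the allocation nor in the listed primary model.

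With few patients per hospital, a coin toss will leave some hospitals lopsided. Any difference between hospitals then adds noise to the treatment difference that is compared with the margin of 8 MHQ points. The surgeon step is no firm safeguard, because whether and how it is applied depends on numbers known only after recruitment. At stake is some precision and credibility in a non-inferiority trial planned at 80% power.

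**Working it through.** **Inputs from section 4.4.** "We used a one-sided significance level of 0.025 and a power of 80% with a standard deviation (SD) of 15"; margin 8; 57 per arm, 114 in total; 126 randomised.

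**Inputs assumed.** The number of hospitals, taken as 6 to 15 of equal size, and the intraclass correlation (ICC), meaning the share of MHQ variance that lies between hospitals, taken as 0 to 0.15.

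**1. The plan's own figure.** Noncentral t, true difference 0, standard error 15 × √(1/n₁ + 1/n₂): 56 per arm gives 79.9% power and 57 per arm gives 80.6%. The 114 is therefore reproduced exactly. 114 × 1.10 = 125.4, rounded up to 126.

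**2. Arm sizes under simple randomisation.** Binomial(114, 0.5), with power computed for each split: 80.6% at 57:57, 80.2% on average and 79.4% at the 95% limit (47:67). The average cost is 80.6 − 80.2 = 0.4 points.

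**3. Hospital mix (assumed equal hospitals).**
- 6 hospitals of 21: P(a given hospital splits 70:30 or worse) = 0.078; P(at least one) = 1 − (1 − 0.078)⁶ = 39%.
- 10 hospitals of 12: P(9:3 or worse) = 2 × (1 + 12 + 66 + 220)/4096 = 0.146; P(at least one) = 1 − 0.854¹⁰ = 79%.
- 15 hospitals of 8: P(6:2 or worse) = 2 × (1 + 8 + 28)/256 = 0.289; P(at least one) = 1 − 0.711¹⁵ = 99%.

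**4. Effect on the estimate.** Chance hospital imbalance moves the treatment difference with an SD of about 15 × √ICC × √(4/114). That is 0.6 points at ICC 0.05, 0.9 at 0.10 and 1.1 at 0.15, against a margin of 8.

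**5. Ceiling on the gain.** Suppose all between-hospital variance were removed at 57:57, with no loss of degrees of freedom. The SD becomes 15 × √(1 − ICC), and power rises from 80.6% to 82.5%, 84.5% and 86.5% at ICC 0.05, 0.10 and 0.15.

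**6. Simulation with a fixed hospital effect.** 114 evaluable patients, 4,000 replicates per setting, simulation error about 0.6 points. The stratified scheme used blocks of 2 or 4. Power, %:

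| Hospitals | ICC | Simple, no hospital term | Simple, fixed hospital effect | Stratified, fixed hospital effect |
|---|---|---|---|---|
| 6 | 0 | 80.2 | 78.4 | 79.4 |
| 6 | 0.05 | 80.6 | 80.4 | 83.0 |
| 6 | 0.10 | 79.8 | 81.9 | 84.6 |
| 12 | 0 | 79.8 | 75.9 | 78.9 |
| 12 | 0.05 | 80.6 | 77.9 | 82.9 |
| 12 | 0.10 | 80.1 | 80.5 | 83.9 |

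Under simple allocation with 12 small hospitals, a fixed hospital effect can lose power: 79.8 − 75.9 = 3.9 points at ICC 0 and 80.6 − 77.9 = 2.7 points at ICC 0.05.

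**7. Simulation with a random hospital intercept.** 6 or 12 hospitals, ICC 0.05 to 0.15. Under simple allocation the intercept adds about 0.5 to 4 power points. With stratified allocation as well, power is about 82% to 86%, against 79% to 83% with neither.

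**8. Type I error.** True difference at the margin, simple allocation, no hospital term: simulated one-sided error 0.021 to 0.032 (nominal 0.025, simulation error about 0.0025).

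The simulations compare the two arms without the section 7 covariates, so the differences between columns matter more than the levels.

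**The case against.** **What stands on the other side.** Simple randomisation is the least predictable scheme. In an unblinded trial where the hand surgeon or site investigator obtains consent, that is a real merit. Under hospital-level blocks of 2, 4 and 6, a recruiter who knows past local allocations and always guesses the arm that is behind is right about 69% of the time, against 50% for a coin toss. Allocating after consent does not prevent selective invitation. A call for stratification that treats it as costless would be wrong.

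The gain also rests on assumptions about hospital number and ICC. Section 5.1 foresees a consensus hand-therapy protocol across hospitals, and the model already includes therapy duration, so the ICC that remains may be small. A statistical analysis plan could add a hospital term; but the allocation scheme is fixed in the protocol, and section 7 names its covariates.

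**Stronger readings that the document does not support.**
- *Arms too small.* Section 4.4 says "Each treatment arm will need 57 patients", and with 126 coin tosses the smaller arm is below 57 in 24.7% of trials even before dropout. But the other arm is then larger: 56:70 gives 83.9% power and 52:74 gives 83.3%, both above the 80.6% at 57:57.
- *A post-hoc surgeon correction, or an admitted surgeon effect.* The step is written in advance; it is conditional. The text plans a possible correction and asserts no effect.
- *Site-dependent outcome measurement.* The primary MHQ is completed by the patient, by post or online. The site's head investigator measures secondary functional outcomes.
- *Surgeons seen in one arm only add nothing.* That holds for fixed surgeon effects, and section 7 does not say they are fixed. Nor would stratifying by hospital balance surgeons within a hospital.

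**Conclusion.** The point holds as a moderate matter of efficiency and credibility. The protocol fixes unrestricted allocation, leaves hospital out of its listed primary model, and offers only a surgeon step whose use depends on realised numbers. With hospitals of 8 to 21 patients, some lopsided hospitals are likely, though with few large hospitals this is far from certain.

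The loss is about 1 to 5 power points if 5% to 15% of the variance lies between hospitals, and essentially nothing to gain if that share is zero. Both the hospital number and the share are assumptions. A reader might infer that the non-inferiority test is invalid. It is not: randomisation keeps the comparison unbiased, the simulated type I error shows no clear inflation, and power without the change stays near the planned 80%. The required sample size does not change.

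**What to change.** 1. **Analysis, whatever the allocation scheme.** In section 7, add hospital as a random intercept to the primary mixed model. Avoid a fixed hospital effect if hospitals are many and small and allocation stays simple, because it can lose power. Keep the surgeon correction as a sensitivity analysis, with its rule fixed before any outcome comparison: which surgeon counts as the treating surgeon in each arm, the minimum numbers needed, and whether the effect is fixed or random. The cost is one model term and a few sentences, and it can be done even if enrolment is complete.

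2. **Allocation, for patients still to be enrolled.** Amend sections 3 and 6.2 to concealed 1:1 allocation in Castor EDC, stratified by hospital. Use randomly varying block sizes not disclosed to sites, preferably without blocks of 2, or minimisation with a random element. The cost is a Castor setting, a short amendment and some loss of unpredictability, which leaving out blocks of 2 reduces only in part. A change during enrolment creates two allocation phases, which the report should describe.

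If the investigators judge unpredictability to be worth more than the few power points, part 1 alone is a reasonable outcome, with the reason for keeping simple randomisation stated in section 6.2.

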4. STUDY POPULATION

4.1 Population (base)

Adult patients presenting at the emergency department (ED) with a sustained trauma to the thumb, resulting in acute pain and swelling around the MCP joint. The diagnosis of an acute complete UCL rupture, including Stener Lesions, needs to be confirmed by the surgeon by physical examination at the first outpatient clinic visit or directly at the ED

4.2 Inclusion criteria

In order to be eligible to participate in this study, a subject must meet all of the following criteria:

- Patients 18 years and older
- Dutch or English speaking patients
- Patients with an acute complete UCL rupture, with or without a Stener Lesion, diagnosed using physical examination, performed by the hand surgeon. When providing radically directed force to the proximal phalanx (radial deviation stress) as the thumb metacarpal is stabilized in a neutral position, criteria 1 AND 2 must be present to confirm the diagnosis of a complete UCL rupture:
 - no firm endpoint in the MCP joint AND
 - at least more than 35 degrees of laxity in the MCP joint, measured with the MCP joint in 30 degrees of flexion OR more than 15 degrees difference in laxity compared with the uninjured side.

